5.7.3 Supportive Care Guidelines for Pneumonitis

Subjects with symptomatic pneumonitis should immediately stop receiving pembrolizumab and have an evaluation. The evaluation may include bronchoscopy and pulmonary function tests to rule out other causes such as infection. If the subject is determined to have study drug associated pneumonitis, the suggested treatment plan is detailed in Table 7.

Table 7. Recommended Approach to Handling Pneumonitis

Study Drug Associated Pneumonitis	Withhold/Discontinue Pembrolizumab?	Supportive Care
Grade 1 (asymptomatic)	No action	Intervention not indicated
Grade 2	Withhold pembrolizumab, may return to treatment if improves to Grade 1 or resolves within 12 weeks	Systemic corticosteroids are indicated. Taper if necessary.
Grade 3 and Grade 4	Discontinue pembrolizumab	Systemic corticosteroids are indicated. The use of infliximab may be indicated as appropriate. Refer to the Event of Clinical Interest and Immune-related Adverse Event Guidance Document (Section 12) for additional recommendations.

For grade 2 pneumonitis that improves to \leq grade 1 within 12 weeks, the following rules should apply:

- First episode of pneumonitis
 - May increase dosing interval by one week (q 4 weeks) in subsequent cycles
- Second episode of pneumonitis – permanently discontinue pembrolizumab if upon rechallenge subject develops pneumonitis \geq grade 2

5.8 Diet/Activity/Other Considerations

5.8.1 Diet

Subjects should maintain a normal diet unless modifications are required to manage an AEs such as diarrhea, nausea or vomiting, mucositis, or dysphagia. Consultation with nutrition during radiation therapy is strongly recommended.

5.8.2 Contraception

Pembrolizumab may have adverse effects on a fetus in utero. Furthermore, it is not known if pembrolizumab has transient adverse effects on the composition of sperm. Non-pregnant, non-breast-feeding women may be enrolled if they are willing to use 2 methods of birth control or are considered highly unlikely to conceive. Highly unlikely to conceive is defined as 1) surgically sterilized, or 2) postmenopausal (a woman who is \geq 45 years of age and has not had menses for greater than 1 year will be considered postmenopausal), or 3) not heterosexually active for the duration of the study. The two birth control methods can be either two barrier methods or a barrier method plus a hormonal method to prevent pregnancy. Subjects should start using birth control from the screening visit throughout the study period up to 120 days after the last dose of study therapy.

The following are considered adequate barrier methods of contraception: diaphragm, condom (by the partner), copper intrauterine device, sponge, or spermicide. Appropriate hormonal contraceptives will include any registered and marketed contraceptive agent that contains an estrogen and/or a progestational agent (including oral, subcutaneous, intrauterine, or intramuscular agents).

Subjects should be informed that taking the study medication may involve unknown risks to the fetus (unborn baby) if pregnancy were to occur during the study. In order to participate in the study they must adhere to the contraception requirement (described above) for the duration of the study and during the follow-up period defined in Section 7.2.2-Reporting of Pregnancy and Lactation to the Sponsor and to Merck. If there is any question that a subject will not reliably comply with the requirements for contraception, that subject should not be entered into the study.

5.8.3 Use in Pregnancy

If a subject inadvertently becomes pregnant while on treatment with pembrolizumab, the subject will immediately be removed from the study. The site will contact the subject at least monthly and document the subject's status until the pregnancy has been completed or terminated. The outcome of the pregnancy will be reported to the sponsor and to Merck without delay and within 24 hours if the outcome is a serious adverse experience (e.g., death, abortion, congenital anomaly, or other disabling or life-threatening complication to the mother or newborn). The study investigator will make every effort to obtain permission to follow the outcome of the pregnancy and report the information to the sponsor and to Merck. If a male subject impregnates his female partner, the study personnel at the site must be informed immediately, and the pregnancy must be reported to the sponsor and to Merck, and followed as described above and in Section 7.2.2.

5.8.4 Use in Nursing Women

It is unknown whether pembrolizumab is excreted in human milk. Since many drugs are excreted in human milk, and because of the potential for serious adverse reactions in the nursing infant, subjects who are breast-feeding are not eligible for enrollment.

5.9 Subject Withdrawal, Replacement and Criteria for Early Trial Termination

5.9.1 Subject Withdrawal/Discontinuation Criteria

Subjects may withdraw consent at any time for any reason or be dropped from the trial at the discretion of the investigator should any untoward effect occur. In addition, a subject may be withdrawn by the Investigator if enrollment into the trial is inappropriate, the trial plan is violated, or for administrative and/or other safety reasons. Specific details regarding discontinuation or withdrawal are provided in Section 7.1.4 – Other Procedures.

A subject must be discontinued from the trial treatment for any of the following reasons:

- The subject withdraws consent.
- Confirmed radiographic disease progression. See Section 7.1.2.6
- Unacceptable adverse events as described in Section 5.4.2
- Intercurrent illness that prevents further administration of treatment
- Investigator's decision to withdraw the subject
- The subject has a confirmed positive serum pregnancy test
- Noncompliance with trial treatment or procedure requirements
- The subject is lost to follow-up

- Completed 24 months of treatment with pembrolizumab
 - Note: 24 months (104 weeks) of study medication is calculated from the date of first dose. Subjects who stop pembrolizumab after 24 months may be eligible for up to 12 months of additional study treatment if they progress after stopping study treatment provided they meet the requirements detailed in Section 7.1.5.2.1.
- Administrative reasons

The End of Treatment and Follow-up visit procedures are listed in Section 6 (Protocol Flow Chart) and Section 7.1.5 (Visit Requirements). After the end of treatment, each subject will be followed for 30 days for adverse event monitoring (serious adverse events will be collected for 90 days after the end of treatment as described in Section 7.2.3.1). Subjects who discontinue for reasons other than progressive disease will have post-treatment follow-up for disease status until disease progression, initiating a non-study cancer treatment, withdrawing consent or becoming lost to follow-up. After documented disease progression, each subject will be followed by telephone for overall survival until death, withdrawal of consent, or the end of the study, whichever occurs first.

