5.3.2 Radiation Therapy Toxicity Evaluation and Dose Modification

All acute radiation toxicities (defined as toxicities occurring within 90 days from therapy start) will be graded according CTCAE v.4.0. During treatment with reirradiation plus concurrent chemotherapy, Grade 3, therapy-induced, acute non-hematologic toxicities have been observed in upwards of 30-50% patients.^{56 30-32, 34} Common acute radiation adverse events in this patient

population include mucositis, pain, esophagitis, dysphagia, fatigue, weight loss, regional alopecia, xerostomia, hoarseness, transient ear discomfort, dysgeusia, and skin erythema and desquamation within the treatment fields. Nutritional evaluation prior to the initiation of therapy is highly recommended. Placement of a prophylactic gastrostomy tube or PEG tube during therapy will be at the discretion of the treating physician. In the case of severe weight loss, the use of tube feedings is encouraged as it is anticipated to minimize further treatment interruptions.

Late toxicities (defined as toxicities occurring after 90 days of therapy initiation) will be graded according to CTCAE v4.0. Late toxicities can include permanent xerostomia and occasionally persistent dysphagia. Less common long-term treatment adverse events include: hypothyroidism, loss of hearing, chronic swallowing dysfunction requiring permanent feeding tube, and cervical fibrosis. Rarer late radiation adverse events include: mandibular osteoradionecrosis and cervical myelopathy. Special attention should be directed in follow-up exams to any numbness or paresthesia, particularly in the first 6-12 months of follow-up. There is a relatively small, but real risk of carotid rupture in patients whose tumors overlap the carotid artery. Most of these events have occurred in association with active tumor in this region and may not necessarily be due to adverse effects of treatment.

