7.1.2 Clinical Procedures/Assessments

7.1.2.1 Adverse Event (AE) Monitoring

The investigator or qualified designee will assess each subject to evaluate for potential new or worsening AEs as specified in the Trial Flow Charts and more frequently if clinically indicated. Adverse experiences will be graded and recorded throughout the study and during the follow-up period according to NCI CTCAE Version 4.0 (see Section 12). Toxicities will be characterized in terms of seriousness, causality, toxicity grading and action taken with regard to trial treatment.

All AEs of unknown etiology associated with pembrolizumab exposure should be evaluated to determine if it is possibly an event of clinical interest (ECI) of a potentially immunologic etiology (irAE). See Section 5.7.2 and the separate guidance document in the study appendices regarding the identification, evaluation and management of AEs of a potential immunological etiology.

Please refer to section 7.2 for detailed information regarding the assessment and recording of AEs.

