7.1.5.3 Post Pembrolizumab Treatment Visits

7.1.5.3.1 Safety Follow-Up Visit

The mandatory Safety Follow-Up Visit should be conducted approximately 30 days after the last dose of pembrolizumab or before the initiation of a new anti-cancer treatment, whichever comes first. All AEs that occur prior to the Safety Follow-Up Visit should be recorded. Subjects with an AE of grade > 1 will be followed until the resolution of the AE to grade 0-1 or until the beginning of a new anti-neoplastic therapy, whichever occurs first. SAEs that occur within 90 days of the end of treatment or before initiation of a new anti-cancer treatment should also be followed and recorded.

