7.2.3 Abnormal Test Findings

An abnormal test finding will be classified as an *adverse event* if one or more of the following criteria are met:

- The test finding is accompanied by clinical symptoms.
- The test finding necessitates additional diagnostic evaluation(s) or medical/surgical intervention; including significant additional concomitant drug treatment or other therapy.
 - **Note:** simply repeating a test finding, in the absence of any of the other listed criteria, does not constitute an AE.
- The test finding leads to a change in study dosing or discontinuation of subject participation in the clinical study.

All adverse events will be recorded from the time the consent form is signed through 30 days following cessation of treatment and at each examination on the adverse event case report forms/worksheets. The reporting timeframe for adverse events meeting any serious criteria is described in section 7.2.3.1.

Adverse events will not be collected for subjects as long as that subject has not undergone any protocol-specified procedure or intervention. If the subject requires a blood draw, fresh tumor biopsy etc., the subject is first required to provide consent to the main study, and AEs will be captured according to guidelines for standard AE reporting.

7.2.3.1 Definition of an Overdose for This Protocol and Reporting of Overdose to Merck

For purposes of this trial, an overdose will be defined as any dose exceeding the prescribed dose for pembrolizumab by 20% over the prescribed dose. No specific information is available on the treatment of overdose of pembrolizumab. In the event of overdose, the subject should be observed closely for signs of toxicity. Appropriate supportive treatment should be provided if clinically indicated.

If an adverse event(s) is associated with ("results from") the overdose of a Merck product, the adverse event(s) is reported as a serious adverse event, even if no other seriousness criteria are met.

If a dose of Merck's product meeting the protocol definition of overdose is taken without

any associated clinical symptoms or abnormal laboratory results, the overdose is reported as a non-serious Event of Clinical Interest (ECI), using the terminology “accidental or intentional overdose without adverse effect.”

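### The windows for collecting adverse events contradict each other, and how long late toxicity is captured depends on response

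*Combined protocol and SAP*

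**What the plan says.** Two sets of rules cover adverse events (AEs) once treatment ends.

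- **Fixed windows.** Section 5.9.1 states that "each subject will be followed for 30 days for adverse event monitoring (serious adverse events will be collected for 90 days after the end of" study therapy). Section 7.1.5.3.1 places the safety visit about 30 days after the last pembrolizumab dose, or earlier if new anticancer treatment starts, and adds "All AEs that occur prior to the Safety Follow-Up Visit should be recorded". It limits serious adverse events (SAEs) to 90 days or the start of new treatment, without saying which governs.
- **Collection through follow-up.** Section 7.1.2.1 says "Adverse experiences will be graded and recorded throughout the study and during the follow-up period". Section 7.2.3 records AEs "through 30 days following cessation of treatment and at each examination on the adverse event case report forms/worksheets". For ongoing events, Section 7.1.5.3.1 itself goes further: "Subjects with an AE of grade > 1 will be followed until the resolution of the AE to grade 0-1", or until new therapy. Chart 6.2 (complete response, CR, or 24 months completed without progression) marks AE review at 3, 6, 9, 12, 18 and 24 months after the last dose and then annually, ending at progression or non-protocol therapy. Chart 6.4 (progression, toxicity or other discontinuation) marks it at 30 days, 3 months and 6 months after the last dose, and not in survival follow-up.

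Late toxicity runs on another clock. Section 5.3.2 states: "Late toxicities (defined as toxicities occurring after 90 days of therapy initiation) will be graded according to CTCAE v4.0". Safety is the first secondary objective (Section 3.2), and Section 8.2.1 commits to reporting toxicity for the whole cohort. Section 8 gives no time origin, horizon or method for late toxicity.

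**The concern.** The fixed windows are counted from the end of drug treatment, but late radiation toxicity is counted from the start of therapy. Section 5.3.2 names osteoradionecrosis, cervical myelopathy and carotid rupture among the late or rarer risks. A site that follows 5.9.1 and 7.1.5.3.1 would stop collecting new events soon after late toxicity becomes possible; a site that follows the charts would continue. Because drug duration depends on response, so does the length of capture.

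With 48 patients, one arm and a historical comparison, the recorded rate is the whole of the safety evidence. A crude percentage would mix patients observed for very different times, and possibly under different rules at different sites.

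**Working it through.** The plan gives no figure to reproduce here, so the check is date arithmetic followed by a comparison of the sections.

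**Inputs**
- Cycles last 21 days (Chart 6.1), so day 1 of cycle k is 1 + 21(k − 1).
- Late toxicity starts after day 90 (Section 5.3.2).
- Literal windows: 30 days for AEs and 90 days for SAEs (Section 5.9.1).
- Last dated AE review: 6 months, taken as 183 days (Chart 6.4); 24 months, taken as 730 days (Chart 6.2).
- Last dose for CR or progressive disease (PD) at the 3-month scan: cycle 6 to 8 (assumption). Cycle 6 is the last planned before the week-17 scan. Footnote 9 of Chart 6.1 continues drug until the response is confirmed, at the earliest 4 weeks later (Section 7.1.2.6.4.2). Cycle 6 is day 1 + 5 × 21 = 106; cycle 8 is day 1 + 7 × 21 = 148.
- Last dose for partial response or stable disease (PR/SD) treated to the 104-week limit: 1 + 34 × 21 = day 715, about week 103.

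**Results** (late-toxicity days = end of capture − 90)

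| Path and rule | End of capture (day) | Late-toxicity days |
|---|---|---|
| CR or PD, literal AE window | 106 + 30 = 136 to 148 + 30 = 178 | 46 to 88 |
| CR or PD, literal SAE window | 106 + 90 = 196 to 148 + 90 = 238 | 106 to 148 |
| PR/SD to week 103, literal AE window | 715 + 30 = 745 | 655 |
| PD, Chart 6.4 | 106 + 183 = 289 to 148 + 183 = 331 | 199 to 241 |
| Sustained CR, Chart 6.2 | 106 + 730 = 836 to 148 + 730 = 878, then annual | 746 to 788, then more |

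For a patient who stops for toxicity after cycle 2 (day 22), the literal AE window closes at 22 + 30 = day 52, before late toxicity begins. Chart 6.4 would run to 22 + 183 = day 205, and Chart 6.2 to 22 + 730 = day 752.

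**Sections side by side**
1. *SAEs.* Sections 5.9.1 and 7.2.3 both refer to 7.2.3.1 for the SAE timeframe, but 7.2.3.1 covers overdose. Section 7.2.4.1 requires at least 90 days of outcome follow-up for SAEs, which is not a window for collecting new ones. Section 7.2.4.2 ends reporting of events of clinical interest at 90 days or at new therapy.
2. *After progression.* Section 5.9.1 gives telephone contact for survival. Chart 6.4 and Section 7.1.5.4.1 give visits, with AE review to 6 months after the last dose.
3. *Stopping for toxicity.* The title of Chart 6.4 includes these patients; Section 7.1.5.4 sends them to Chart 6.2.
4. *CR with later relapse and no retreatment.* Chart 6.2 ends at progression. Chart 6.4 visits are timed from the last dose, so once relapse comes after the 6-month visit no AE review remains scheduled.

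**The case against.** The strongest reply is that the protocol does provide for later capture. Section 5.9.1 itself refers to Section 6 for follow-up procedures. Section 7.2.2 requires all observed or volunteered events to be recorded, serious or not, and Section 7.2.5 requires each to be assessed for seriousness. A serious event found at a chart visit is therefore recordable. Late toxicity is also not the main safety question: Section 8.1 speaks of the early profile, and the radiation hypothesis in Section 3.2 concerns acute toxicity.

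Much of this stands, and it rules out three stronger readings that a reader might infer.

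- *AEs are collected for only 30 days and SAEs for only 90.* Sections 7.1.2.1 and 7.2.3 and the charts say otherwise for AEs. For SAEs the text is unclear rather than plainly closed.
- *A carotid event at month 9 in a CR patient would be missed.* Month 9 is about day 9 × 30.44 = 274, which is 168 days after a day-106 last dose and before the 6-month review at day 289. It is lost only under the literal windows.
- *Under-counting is worst in those who live longest without progression.* Under the literal text PR/SD patients have the longest capture, and under the charts review ends earliest after progression.

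In addition, the 6-to-12-month attention in Section 5.3.2 concerns numbness and paresthesia at follow-up exams. It is not a stated window for carotid rupture or osteoradionecrosis, and it favors continued capture.

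The reply does not say which rule prevails, repair the SAE reference, or remove the dependence of observation time on outcome.

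**Conclusion.** The point holds as a conflict between stated rules, together with outcome-dependent observation of late toxicity. Under the literal windows, a CR or PD patient has 46 to 88 late-toxicity days for AEs, against 655 for a PR/SD patient treated to about week 103. Under the charts, a patient with PD has 199 to 241 days, against 746 to 788 plus annual visits in sustained CR. The imbalance exists under either rule, but it falls on different patients.

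These figures assume no dose delays, a last dose at cycle 6 to 8 for CR or PD, and a study still open at the later visits. The planned duration of about 36 months could cut the last Chart 6.2 visits short. The documents do not show that late events will in fact be lost; that depends on which rule the sites apply. The primary endpoint and the 7-week stopping rule are unaffected.

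**What to change.** 1. Reconcile Sections 5.9.1, 7.1.5.3.1, 7.1.5.4 and 7.2.3 with Charts 6.2 and 6.4. Give one AE follow-up schedule after progression and one for patients who stop for toxicity.
2. Replace the two references to Section 7.2.3.1 with a section that states the SAE collection window.
3. State that radiation-attributed events of grade 3 or higher, and radiation-attributed SAEs, are recorded at every scheduled follow-up visit regardless of time since the last pembrolizumab dose.
4. Add to Section 8 that late toxicity is reported from the start of radiation as cumulative incidence, with death as a competing event and censoring at the last AE assessment. Show observation time by response group, since censoring after progression may be informative.

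The cost is protocol wording, slightly more data entry and some additional SAE reporting. The visits and their AE review are already in the charts.

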5.10 Subject Replacement Strategy

A subject that withdraws from the trial for reasons other than toxicity, progression of disease or death and withdraws before the initial efficacy evaluation (PET/CT done at 3 months after completion of radiation) can be replaced. These cases will be recorded and accounted for in the report of the trial.

5.11 Criteria for Early Trial or Performance Site Termination

Early trial termination will be the result of meeting one of the criteria specified below:

- 1 Quality or quantity of data recording is inaccurate or incomplete.
- 2 Poor adherence to protocol and regulatory requirements.
- 3 Incidence or severity of adverse drug reaction in this or other studies indicates a potential health hazard to subjects.
- 4 If acute radiation toxicity threshold is crossed by the first 20 patients enrolled as detailed in Section 8.0, discussion with Merck will ensue and trial may be closed early.
- 5 Plans to modify or discontinue the development of the study drug.

In the event of Merck's decision to no longer supply study drug, ample notification will be provided so that appropriate adjustments to subject treatment can be made.

6.0 TRIAL FLOW CHARTS

6.1 Initial Treatment Phase

Trial Period:	Screening Day - 28 to -1	Radiation + Pembrolizumab Treatment ¹		Pembrolizumab Monotherapy (Weeks 6-16) ²		3 Months Post Radiation Imaging ³	
Radiation Treatment (1.2Gy BID Monday–Friday x25 days)		Treatment with radiation 1.2Gy BID Monday –Friday X 25 treatment days (weeks 1-5)					
Pembrolizumab Treatment (Day 1 of each 21 Day Cycle):		Cycle 1, Day 1	Cycle 2, Day 1	Day 1, Cycles 3-6		Week 17 +/- 7 days	
Scheduling Window (Days):		+ 1 day	+1 day	+/- 3 days			
Administrative Procedures							
Informed Consent	X						
Inclusion/Exclusion Criteria		X					
Demographics and Medical History	X						
Prior and Concomitant Medications	X	X	X	X	X	X	X
SCCHN History and Treatment	X						
Pembrolizumab Treatment Administration		X	X	X	X	X	X ⁹
Clinical Procedures/Assessments							
Review Adverse Events ¹	X	X	X	X	X	X	X
Full Physical Examination	X			X			X
Directed Physical Examination ¹		X	X		X	X	X
Vital Signs and Weight ⁵	X	X	X	X	X	X	X
ECOG Performance Status	X	X	X	X	X	X	X
Dental Evaluation ⁶	X						
12 Lead EKG	X					X	
Laboratory Procedures/Assessments: analysis performed by LOCAL laboratory							
Pregnancy Test – Urine or Serum β-HCG ⁷	X						
PT/INR and aPTT ¹²	X						
CBC with Differential ⁸	X	X	X ¹⁵	X	X	X	X

Trial Period:	Screening Day - 28 to -1	Radiation + Pembrolizumab Treatment ¹		Pembrolizumab Monotherapy (Weeks 6-16) ²		3 Months Post Radiation Imaging ³	
Radiation Treatment (1.2Gy BID Monday–Friday x25 days)		Treatment with radiation 1.2Gy BID Monday –Friday X 25 treatment days (weeks 1-5)					
Pembrolizumab Treatment (Day 1 of each 21 Day Cycle):		Cycle 1, Day 1	Cycle 2, Day 1	Day 1, Cycles 3-6			
Scheduling Window (Days):		+ 1 day	+1 day	+/- 3 days		+/- 7 days	
Comprehensive Serum Chemistry Panel ¹⁴	X	X	X ¹⁵	X	X	X	X
Urinalysis	X						X
T3, FT4 and TSH	X						X
Hepatitis C Ab ¹⁶	X						
HBsAg, HBsAb	X						
HIV 1/2 Antibodies	X						
Efficacy Measurements							
PET/CT ³	X						X ⁹
Tumor Biopsies/Archival Tissue Collection/Correlative Studies Blood							
Archival or Fresh Tissue Collection ¹⁰	X						X ¹³
Correlative Studies Blood Collection/Blood for Future Biomedical Research ^{4, 10}		X		X			X
Patient Reported Outcome Measures¹¹							
EORTC QLQ C-30	X	X	X	X	X	X	X
EORTC QLQ-H&N35	X	X	X	X	X	X	X

1. During radiation treatment, patients will be evaluated weekly with a directed physical exam and toxicity evaluation (patients will be evaluated more frequently if clinically indicated). The first dose of pembrolizumab should be given on the first day of radiation (+ 1 day) Radiation treatment can begin Monday through Wednesday. Doses of pembrolizumab during radiation treatment can be given before or after the first radiation treatment of the day.

2. During the time period between completion of Radiation + Pembrolizumab Treatment and the 3 Months Post Radiation Imaging, the patient will be seen at Weeks 6 and 7, then at least once a month by a radiation oncologist. The patient will be seen before each pembrolizumab dose by a medical oncologist.

3. Baseline tumor evaluation and tumor efficacy assessment at 3 months after completion of reirradiation will be with PET/CT. CT will include diagnostic CT with contrast of neck/neck/abdomen/pelvis. If the investigator feels that MRI will be the best way to follow the patient's head and neck disease subsequently, then an MRI of the neck should be done at baseline as well. However, CT scan is encouraged over MRI. For the initial PET/CT done during the screening procedures, the diagnostic CT scans need to be done within 28 days of the start of therapy while the PET can be done within 42 days of start of therapy.
4. Blood (approximately 2 teaspoons) will be drawn for correlative studies. Tumor and additional blood (approximately 2 teaspoons) for future biomedical research (FBR) is optional, but patient consent must be obtained prior to sample collection. If a patient does not consent for FBR then only blood for correlative studies will be drawn. Blood draws for correlative studies and FBR will be into a Na Heparin "green top" tube (1 tube for each). They will be drawn prior to dosage of pembrolizumab at first and third cycle, and additionally at week 17 visit and at visit at time of progression.
5. Vital signs to include temperature, pulse, respiratory rate, blood pressure, and oxygen saturation as measured by pulse oximeter. Height will be recorded at screening visit only.
6. Prior to radiation therapy a dental evaluation will be done if recommended by treating radiation oncologist. Extraction of extensively diseased teeth should be carried out with conservation of restorable teeth where possible. At least 10 days should be allowed for healing of gingivae post-extraction. Because dental evaluation would be required for reirradiation as part of standard of care this evaluation/treatment can begin before consent for the trial.
7. For women of reproductive potential, a urine pregnancy test will be performed within 72 hours prior to first dosage of pembrolizumab. If a urine pregnancy result can't be confirmed as negative, then a serum pregnancy test will be required. Pregnancy testing may be repeated if pregnancy is suspected.
8. CBC to include white blood cells, hgb/hct, platelets and differential. CBC as part of screening for organ function (inclusion criteria # 13) is required to be done within 21 days of start date
9. Tumor imaging will determine the subsequent study treatment plan. Definition of response is detailed in section 7.1.2.6. Subjects with a complete response (CR), partial response (PR), and progressive disease (PD) will require confirmation by repeat CT scan. Subjects will remain on pembrolizumab following section 6.3 until response confirmation. Subjects with confirmed CR will follow Chart 6.2. Subjects with confirmed partial response **or who have** stable disease will **continue** to follow Chart 6.3. Subjects with confirmed progressive disease will follow Chart 6.4. See section 7.1.2.6 for all details on definitions of response.
10. Provide adequate tissue (core or incisional/excisional biopsy) prior to starting study treatment. This tissue will be used for PD-L1 analysis. Fresh tissue or archival tissue sample can only be used. If adequate tissue cannot be safely obtained than the patient may still be able to be enrolled on the trial after discussion with the study principal investigator, as long as FNA was done to confirm recurrent/second primary HNSCC. If the subject signs the Future Biomedical Research (FBR) consent, any leftover tissue that would ordinarily be discarded at the end of the main study will be retained for FBR.
11. Patient Reported Outcome Measures will be completed by the patient. The EORTC QLQ C-30 should be completed first.
12. Coagulation studies will be repeated as clinically necessary.
13. A repeat biopsy may be needed to confirm disease status. See section 7.1.2.6.4 Assessment of Disease
14. Comprehensive serum chemistry panel is done as part of screening for organ function (inclusion criteria #13) is required within 21 days of start date
15. Starting with cycle 2 of pembrolizumab, CBC and CMP required prior to giving dosage can be done within 48 hours of dosage.
16. If Hep C Ab is positive a Hep C virus RNA PCR can be checked. If the Hep C virus RNA PCR is negative then the patient does not have active Hep C and therefore would still qualify for the trial.

6.2 Follow Up Phase for Patients Who Achieve a CR at Any Point During the Study or Who Complete Up to 24 Months of Pembrolizumab Without Progression of Disease.¹

Trial Period: Follow Up	Visits during the first year after the last dosage of pembrolizumab ²						Annually after 24 M visit
	3M	6M	9M	12M	18M	24M	
Visit Window	+/- 2Wk	+/- 2Wk	+/- 2Wk	+/- 2Wk	+/- 2Wk	+/- 2Wk	+/- 2 weeks
Clinical Procedures/Assessments							
Concomitant Medication Review	X	X	X	X	X	X	X
Adverse Events	X	X	X	X	X	X	X
ECOG Performance Status	X	X	X	X	X	X	X
Directed Physical Examination	X	X	X	X	X	X	X
Vital Signs and Weight ⁷	X	X	X	X	X	X	X
Efficacy Measurement							
Tumor Imaging ^{4,5}	X	X	X	X	X	X	X ⁸
Laboratory Procedures/Assessments							
Comprehensive Serum Chemistry Panel	X	X	X	X	X	X	X
CBC with Differential	X	X	X	X	X	X	X
T3, FT4 and TSH				X		X	X
Patient Reported Outcomes⁶							
EORTC QLQ C-30	X	X	X	X	X	X	X
EORTC QLQ-H&N35	X	x	X	X	X	X	X

1. Patients will undergo follow up as per this table until progression, withdrawal of consent, initiation of non-protocol anti-cancer treatment(s) or death, whichever occurs first. Definition of "first year" and "second year" are from the time of last pembrolizumab dosage. Patients who recur or progress may be eligible for retreatment discussed in section 7.1.5.2.1.

2. During the first year of follow up patients will be seen at least every 3 months. The patient can be seen more frequently if clinically indicated.

3. During the second year of follow up patients will be seen at least every 6 months. The patient can be seen more frequently if clinically indicated.
4. During the first year of follow up patients will undergo neck CT with IV contrast every 3 months to evaluate for recurrence. CT chest with IV contrast or CXR PA/Lateral will be done at the discretion of the investigator, as clinically indicated. This will be obtained prior to each 3 month visit. If the patient has evidence of recurrence on CT scan, a biopsy will be done. If recurrence is confirmed, the patient can be treated with pembrolizumab again as per the treatment flow chart 6.3. Patients can be retreated with pembrolizumab for up to one year. If the investigator feels that MRI will be the best way to follow the patients head and neck disease subsequently, then an MRI of the neck should be done at baseline as well. However, CT scan is encouraged over MRI.
5. During the second year of follow up patients will undergo neck CT with IV contrast every 6 months to evaluate for recurrence. CT chest with IV contrast or CXR PA/Lateral will be done at the discretion of the treating physician, as clinically indicated. This will be done prior to each 6 month visit. If the patient has evidence of recurrence on imaging, a biopsy will be done. If recurrence is proven, the patient may be eligible to be treated with pembrolizumab again as per table 6.3 below (Treatment phase for patients with PR/SD at 3 months post radiation). Patients can be retreated with pembrolizumab for up to one year. If the investigator feels that MRI will be the best way to follow the patient's head and neck disease subsequently, then an MRI of the neck should be done at baseline as well. However, CT scan is encouraged over MRI.
6. Patient Reported Outcome Measures will be completed by the patient. The EORTC QLQ C-30 should be completed first.
7. Vital signs to include temperature, pulse, respiratory rate, blood pressure, and oxygen saturation as measured by pulse oximeter.
8. Imaging will be done as clinically indicated.

6.3 Treatment Phase for Patients with a Partial Response (PR) or Stable Disease (SD) on Imaging 3 Months Post Completion of Radiation.¹

Trial Phase	Treatment Cycle										Treatment Cycle
	7	8	9	10	11	12	13	14	15		
Treatment Cycle/Scheduled Time (Pembrolizumab Day 1 of each 3-week Cycle)											16 and beyond ²
Scheduling Window (days): +/- 3 days											
Clinical Procedures/Assessments											
Review Adverse Events	X	X	X	X	X	X	X	X	X		
Directed Physical Exam	X	X	X	X	X	X	X	X	X		
Vital Signs and Weight ⁶	X	X	X	X	X	X	X	X	X		
Concomitant Medication Review	X	X	X	X	X	X	X	X	X		
Laboratory Procedures/Assessments											
CBC with Differential	X	X	X	X	X	X	X	X	X		
Comprehensive Serum Chemistry Panel	X	X	X	X	X	X	X	X	X		
Urinalysis ⁵				X			X			X ³	
T3, FT4, TSH ³				X			X			X ³	
Patient reported outcomes											
EORTC QLQ C-30	X		X		X		X		X	X ⁴	
EORTC QLQ-H&N35	X		X		X		X		X	X ⁴	
Efficacy Measurements											
Tumor Imaging ⁵			X ⁵		X ⁵		X ⁵		X ⁵	X ⁵	

1. Patients that develop a complete response during this phase of treatment will be followed as per table 6.2.
2. Patients will continue treatment with pembrolizumab for up to 24 months (from first dosage) or until progression of disease, complete response, discontinuation because of toxicity, or withdrawal from study.
3. Urinalysis and T3, FT4, TSH to be drawn before every 4th cycle (i.e. Cycle 18, Cycle 22, etc.).
4. EORTC QLQ C-30 and EORTC QLQ-H&N35 will be filled out by the patient every other cycle. The EORTC QLQ C-30 should be completed first.
5. Tumor imaging with CT neck and chest with IV contrast will be obtained after each 3rd cycle (or sooner if clinically indicated) Imaging should be reviewed to determine disease status prior to giving every 4th cycle . Definition of response is as per section 7.1.2.6.4. If the investigator feels that MRI will be the best way to follow the patient's head and neck disease subsequently, then an MRI of the neck should be done at baseline as well. However, CT scan is encouraged over MRI.
6. Vital signs to include temperature, pulse, respiratory rate, blood pressure, and oxygen saturation as measured by pulse oximeter.

6.4 Follow Up Phase for Patients with Progressive Disease or Who Discontinue Treatment Because of Toxicity or Any Other Reason (other than completing all eligible cycles of pembrolizumab treatment).

These patients will be taken off of pembrolizumab and enter the follow up phase.

Trial Phase	Safety Follow-up	Follow-up		Survival Follow-up ¹
Time from Last pembrolizumab Dose	30 days	3 months	6 months	Starting at 9 months
Visit	Safety Follow up visit	Follow up visit 1	Follow up visit 2	NA
Scheduling Window	+/- 3 days	+/- 7 days	+/- 7 days	+/- 7 days
Administrative Procedures				
Review Medications	X	X	X	
Subsequent Antineoplastic Therapy	X	X	X	X
Survival Status				X
Clinical Procedures/Assessments				
Review Adverse Events	X	X	X	
ECOG Performance Status	X	X	X	
Directed Physical Exam	X	X	X	
Vital Signs and Weight ³	X	X	X	
Laboratory Procedures/Assessments				
CBC with Differential	X	X	X	
Comprehensive Serum Chemistry Panel	X	X	X	
Patient Reported Outcomes²				
EORTC QLQ C-30	X	X	X	
EORTC QLQ-H&N35	X	X	X	

1. During survival follow-up patients should be contacted by telephone every 12 weeks to assess for survival status until death, withdrawal of consent, or the end of the study, whichever occurs first.
2. The EORTC QLQ C-30 should be completed first.
3. Vital signs to include temperature, pulse, respiratory rate, blood pressure, and oxygen saturation as measured by pulse oximeter.

4.

